11.3 General Considerations

All clinical test results will be listed and summarized by treatment and time with appropriate descriptive statistics (number of observations, mean, median, standard deviation, minimum, and maximum) for continuous measures. Nominal and ordinal scale measures will be summarized with frequency tables, relative risk, and percentages, as appropriate.

11.4 Analysis Populations

The four populations, Safety, Intent-to-Treat (ITT), Per Protocol (PPP) and Full Analysis Population (FAP), are defined below.

11.4.1 Safety Population

The Safety set will include all ITT subjects who received the study treatment. In the event that a subject receives treatment other than what was assigned, safety analyses will be conducted according to the treatment that the subject actually received.

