9. ASSESSMENT OF SAFETY

9.1 Safety Endpoints

All safety endpoints will be assessed from subject randomization through up to 24 months post investigational agent infusion:

- SAE / AE rates
- Occurrence of MACCE including:
 - Cardiovascular death
 - Non-fatal myocardial infarction
 - Non-fatal stroke
 - Cardiac hospitalization due to heart failure
- Target vessel (or other vessel) revascularization post index cardiac catheterization and new or worsening heart failure during the index hospitalization will be tracked as “Adverse Events of Special Interest”.
- Total number of subjects with documented ventricular arrhythmia (sustained and non-sustained VT/VF) throughout the study period.
- Angina pectoris as defined by CCS clinical clarification.
- NYHA Class.
- Telemetry/48 hour Holter monitoring (during hospital admission and at 14 and 30 days, 3 and 6 months follow-up time points) with assessment of occurrence of ventricular arrhythmia.
- TIMI flow and perfusion measurements following intracoronary infusion of the MPC cell solution compared with placebo.
- Physical examinations, monitoring of vital signs (heart rate, respiratory rate, BP, and temperature).
- Results of clinical laboratory tests (hematology, serum chemistry, inflammatory markers), and immunogenicity assays; (flow cytometry Class I and Class II HLA percent reactivity % with specificity, antibovine and antimurine antibody analysis).

AE will be collected after a subject has been randomized. The AE will be graded according to the protocol as “mild”, “moderate”, “severe” and will be classified according to MedDRA.

An independent DSMB will review all safety and relevant clinical data at regular intervals in accordance with their charter. Based on its findings, the DSMB will make recommendations regarding study continuation, enrollment and/or study modification(s).

The primary safety analysis will be performed on the following safety and feasibility parameters up to 30 days post-treatment:

- TIMI flow prior to, during (approximately 50% of total infusion of investigational agent) and following infusion of investigational agent after successful PCI.
- SAE/AE rates.
- Results of clinical laboratory tests (including hematology, serum chemistry, inflammatory markers, flow cytometry anti-HLA Class I and Class II percent reactivity with specificity, antibovine and antimurine antibody analysis).
- Infusion procedure monitoring of vital signs (heart rate, respiratory rate, BP, and temperature).

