9.3 Definitions

Adverse Event (AE) is defined as any untoward medical occurrence in a subject who was treated with an investigational product, and does not necessarily have a causal relationship with the treatment. An AE can therefore be any unfavorable and unintended sign, symptom, or disease, whether or not related to the investigational product.

Serious Adverse Event (SAE) is defined as any untoward medical occurrence that:

- results in death,
- is life-threatening,
- requires inpatient hospitalization or prolongation of existing hospitalization,
- results in persistent or significant disability/incapacity,
- is a congenital anomaly/birth defect, or
- is medically important*

* “Important medical events that may not result in death, be life-threatening, or require hospitalization may be considered a serious adverse drug experience, when based on appropriate medical judgment, they may jeopardize the subject and may require medical or surgical intervention to prevent one of the outcomes listed in this definition.” (CFR 312.32).

Expectedness: An SAE is considered “unexpected” if it is not listed in the IB or is not listed at the specificity or severity that has been observed. The Sponsor is responsible for assessing expectedness of SAE.

Suspected Unexpected Serious Adverse Event reactions (SUSAR) is defined as a SAE event occurring in a subject in an interventional study that is assessed as both causally related to the suspect product under clinical investigation and unexpected per the IB.

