9.5 Relationship to Study Procedure

For each AE, the relationship to the Investigational Agent delivery procedure must be recorded as either **related** (there is a reasonable possibility of a causal relationship between the event and the study procedure) or **not related** (there is not a reasonable possibility of a causal relationship between the event and the study procedure).

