9.7 Procedures for Adverse Event Reporting

AE will be collected only after a subject has been randomized.

All AE (including MACCE), will be recorded by the investigator or designee as part of the study participant's medical history records and on the appropriate case report form. The investigator or designee will evaluate the relationship of the AE to both the investigational agent and study procedure as related, not related, or unknown, and will record the findings, including all pertinent details of the event on the eCRF.

The investigator will take appropriate measures to ensure the subject's well-being and document these interventions on the appropriate eCRF. The DSMB will review these events.

To maintain a consistent and thorough approach to the collection, documentation and assessment of AE, it is essential that investigators provide the Sponsor with the highest level of medical understanding of each event. This means that when describing an event, medical diagnosis is preferred to a list of symptoms. If a diagnosis can be made, which organizes or explains multiple symptoms or a cascade of events, the diagnosis will become the AE and should replace multiple symptoms in the eCRF and study records.

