11.9 Safety Analyses

Review of safety tables, listings and figures will be performed by the medical monitor or designee. The safety tables will allow a view of changes from baseline in findings from 12-lead ECGs, vital signs, clinical laboratory values, and adverse events. No statistical testing will be executed for safety measures.

In this safety study with a limited sample size and projected high subject exclusion rate, the safety analysis will be performed on the Safety population. These analyses will include categorization of events per study phase (before and after cell infusion or assigned treatment) and event attribution as appropriate to the study phase. All analyses will include those at baseline, to 2 weeks post-index procedure.

Safety analyses will be performed on all available data through Visit 12 (Month 24) at the time of conduct of the efficacy analysis. In addition, the final safety analysis will be performed at 24 months for all patients.

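### AE and SAE rates are planned from randomization but analysed only in treated subjects, so they omit a delivery complication that stops the infusion from starting

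*Combined protocol and SAP*

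**What the plan says.** The start of observation is randomization. Section 9.1: "All safety endpoints will be assessed from subject randomization through up to 24 months post investigational agent infusion". Section 9.7: "AE will be collected only after a subject has been randomized". Footnote k to Table 2 says the same, and Visit 1 (Section 6.1.1.1) includes AE/SAE assessment. For each AE, Section 9.5 says "the relationship to the Investigational Agent delivery procedure must be recorded" as related or not related.

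The analysis set is narrower. Section 11.9 says "the safety analysis will be performed on the Safety population", and Section 11.4.1 defines it: "The Safety set will include all ITT subjects who received the study treatment". Section 11.9 also promises "categorization of events per study phase (before and after cell infusion or assigned treatment"). Section 9.3 defines an AE as "any untoward medical occurrence in a subject who was treated with an investigational product".

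Section 9.1 lists SAE/AE rates both as a safety endpoint and in the primary safety analysis to 30 days. Section 4.1 makes the safety and feasibility of intracoronary delivery the primary objective.

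**The concern.** In a drug trial, a treated-only safety set is the usual choice because the harm of interest follows the dose. Here the primary objective concerns delivery into the coronary artery, and attribution to the delivery procedure is collected for every AE. Randomization comes only after a successful, uncomplicated PCI (Section 7.5). An event between randomization and the start of infusion therefore bears on that objective, whether or not the subject is then infused.

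Under the stated definitions, a subject counts in the pre-infusion phase only if infusion later began. Membership of the set depends on what happened during the phase being measured. A complication that ends the procedure before infusion removes its own subject from both numerator and denominator. Read literally, the definition in Section 9.3 goes further: such an event would not be an AE at all, which conflicts with Sections 9.1 and 9.7.

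**Working it through.** **Step 1. Trace a randomized subject whose infusion never starts, through each planned analysis.**

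| Analysis | Population | Subject included? |
|---|---|---|
| AE/SAE rates and pre-/post-infusion phases (11.9) | Safety: randomized and treated (11.4.1) | No |
| Feasibility, TIMI flow (10.1, 11.8) | Full Analysis, confirmed in Per-Protocol; Full Analysis requires infusion initiated (11.4.4) | No in the primary analysis |
| Clinical endpoints: MACCE, Adverse Events of Special Interest, VT/VF, CCS and NYHA class (8.3, 11.8) | All populations, so ITT is included (11.4.2) | Yes, if recorded |

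What is left uncovered is a complication outside the Section 8.3 list, for example a vessel or access-site injury. An event on that list is counted in ITT but is still missing from the AE/SAE rates and from the pre-infusion phase.

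**Step 2. Check that the data would exist.** Section 4.3 has the site enter the termination reason and screening-visit data for a subject withdrawn before infusion, and says the subject does not stay in the study. The Early Termination Visit (6.1.1.13) applies only after infusion. Section 5.3 says all withdrawn subjects are followed until AEs resolve or stabilize. Sections 4.3 and 5.3 do not agree on this subject.

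**Step 3. Denominators.** Section 11.5 gives 105 subjects, and 1:1:1 allocation gives 105/3 = 35 per arm. The total reproduces closely: a two-sample t-test for a 10 ml difference with SD 14 ml, two-sided 5% and 80% power needs 32 per arm; 32/0.96 rounds up to 34, or 102 in all against 105 stated. This figure is not in dispute and serves only as the denominator.

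**Step 4. Scale.** Let k subjects in one arm have a complication that prevents infusion (k is assumed; the documents give no rate). All-randomized rate = k/35; Safety-set rate = 0/(35 − k).

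| k | All randomized | Safety set |
|---|---|---|
| 1 | 1/35 = 2.9% | 0/34 |
| 2 | 2/35 = 5.7% | 0/33 |
| 3 | 3/35 = 8.6% | 0/32 |
| 4 | 4/35 = 11.4% | 0/31 |

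**Step 5. Chance that it happens at all.** With an assumed true rate p among 105 subjects, the expected number is 105p and P(at least one) = 1 − (1 − p)^105.

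| p (assumed) | Expected number | P(at least one) |
|---|---|---|
| 0.5% | 0.5 | 41% |
| 1% | 1.1 | 65% |
| 2% | 2.1 | 88% |
| 4% | 4.2 | 99% |

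**The case against.** The strongest defence is that little is lost.

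- **Serious cardiac events are covered.** Section 11.8 analyses clinical endpoints in every population, so a catheter complication that causes cardiovascular death, MI, stroke or VT/VF is counted in ITT. This stands. A reader might infer that these events appear in no analysis, or that the gravest are the ones lost; Sections 8.3 and 11.8 do not support that.
- **Events are seen.** SAEs are reported within 24 hours whatever their attribution (9.9), and the DSMB reviews acute peri-procedural data, SAEs and other AEs (4.3). This also stands, but case reporting and DSMB review are not the planned AE/SAE rates.
- **The window is short.** Infusion is to start within 30 minutes after PCI (6.1.1.1), and the documents do not say whether the microcatheter is placed before or after randomization. Counts are probably small.
- **The arms are alike before infusion.** No product has been given, the procedure is blinded, and Section 11.9 plans no statistical testing of safety. A reader might infer a biased comparison of MPC with placebo; the documents do not support that.
- **No percentage understatement can be stated.** A reader might put a figure on it: with five delivery events among 105, two of them preventing infusion, 3/103 (2.9%) against 5/105 (4.8%) is 39% lower. But the assumed two-in-five split produces that result, and the documents supply neither count.
- **Another document may fill the gap.** Section 11.2 refers to a SAP still to be finalized, which could add listings for untreated subjects. The text available does not.

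**Conclusion.** The mismatch is in the text and holds in a limited form. The SAE/AE rates and the pre-infusion phase are conditional on infusion having started, although their window opens at randomization and the primary objective is the safety of delivery. For complications outside MACCE, Adverse Events of Special Interest and VT/VF, no planned AE or SAE analysis includes a never-infused subject. For those three categories the ITT clinical-endpoint analysis does, provided the event was recorded before the subject left.

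The quantity affected is the absolute rate of delivery harm. The number of subjects is unknown and probably small; if every randomized subject is infused, nothing is lost. In arms of 35, however, a single event is the difference between 2.9% and zero. The point concerns infusions that never start. Whether a partial infusion counts as having received treatment is not stated in Section 11.4.1 and should be made explicit. This is a correction worth making, not a threat to the trial's conclusions on efficacy or on product against placebo.

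**What to change.** 1. In Sections 11.4.1 and 11.9, report AEs, SAEs and delivery-procedure-related events from randomization to start of infusion in all randomized subjects (ITT, as randomized). Keep the Safety population for events from start of infusion onward, and say whether a started but incomplete infusion qualifies.
2. Reword the AE definition in Section 9.3 so that it starts at randomization, in line with Sections 9.1 and 9.7.
3. Reconcile Section 4.3 with Section 5.3 on the subject withdrawn before infusion, so that it is clear which AE data are captured.

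The cost is wording in a few sections and one extra table. AE/SAE assessment from randomization is already scheduled at Visit 1; any further data collection depends on how item 3 is settled. The reported procedural event rate may be slightly higher.

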11.4.2 Intent-to-Treat Population

The set of Intent-to-Treat (ITT) subjects will include all subjects who are randomly assigned to a treatment at screening, regardless of whether or not the subject receives the study treatment.

11.4.3 Per-Protocol Population

The PPP will include ITT subjects who do not have major protocol violations, and have at least one post-treatment efficacy and safety evaluation.

11.4.4 Full Analysis Population

The Full Analysis Population will include all subjects who are randomized, have undergone PCI and had infusion of study agent (MPCs or Placebo) initiated.

11.5 Determination of Sample Size

To detect a treatment effect of 10.0 ml for LVESV (SD 14 ml), [REDACTED] as well as published clinical data ^{1-3, 58,59}, with a two-sided 5% significance level and a power of 80%, a sample size of 105 subjects will be necessary, given the observed dropout rate of approximately 4%. Of these, approximately 70 will receive MPCs (35 to receive 12.5 M MPC and 35 to receive 25M MPC) and 35 will receive placebo and act as control subjects.

11.6 Background, Demographic and Concomitant Medications

Demographic data, medical history, concomitant disease and concomitant medication will be summarized by means of descriptive statistics (n, mean, SD, median, minimum and maximum) or frequency tables, stratified by treatment.

11.7 Protocol Deviations

Deviations from the protocol including violations of inclusion/exclusion criteria will be assessed as “minor” or “major”. Deviations will be defined prior to un-blinding.

11.8 Efficacy and Feasibility Analyses

Where appropriate, 95% confidence intervals for treatment differences in key feasibility measures will be constructed. Analysis of covariance (ANCOVA) may be used where appropriate to adjust for baseline differences in key continuous feasibility outcome measures and also take the site and the time from onset of AMI symptoms to PCI as covariates in the ANCOVA model. For non-normally distributed measures, the Wilcox-Mann-Whitney test or analysis of variance ANOVA of rank transformed data may be used as an alternative. For categorical measures, relative risks and nominal 95% confidence intervals will be constructed to assess strength of association. The Cochran-Mantel-Haeszel test (CMH) controlled by site and the time from the onset of AMI symptom to PCI will be used for the treatment differences. The primary feasibility analysis will be performed on the FA population, and confirmatory based on PP population.

The primary and secondary efficacy analyses will be performed on ITT, FA, and PP populations. Analysis of clinical endpoints will be performed on all analysis populations.

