4. STUDY OBJECTIVES

4.1 Primary Objective

The primary objective of this study is to determine the safety and feasibility of intracoronary allogeneic, immuno-selected, bone marrow-derived Stro3 MPC delivery in the treatment of subjects with STEMI undergoing primary percutaneous coronary intervention of the LAD coronary artery.

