5. SELECTION AND WITHDRAWAL OF SUBJECTS

The study population will consist of an ‘all-comers’ subject population with a *de novo* anterior AMI who are undergoing primary PCI with stent placement within 12 hours after onset of symptoms, who meet all the inclusion and none of the exclusion study criteria. Enrollment and treatment is anticipated to include approximately 105 subjects at approximately 25 clinical sites. The subjects will be of any race and of either gender.

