7.5 Blinding and Randomization

This is a double blinded study. Each subject will be blinded to his/her assigned treatment. Study blinding will be maintained as described below.

Blinded Study Personnel and Participants

Subjects, Site personnel, Investigators will remain blinded until after all safety follow-up is completed. The DSMB may choose to be unblinded.

Unblinded Study Personnel

Pre-specified unblinded clinical operations and biometrics team members at both the vendor and sponsor will have access to the unblinded efficacy results.

These pre-specified unblinded team members will be identified prior to the analysis being conducted and they will not have any operational responsibility for the conduct of the study.

An independent unblinded statistician from the CRO will support the DSMB by providing Open and Closed Reports to the DSMB independent statistician based on the best available data and other information to the DSMB.

Subjects that are admitted within a maximum of 12 hours after onset of ischemic cardiac symptoms who are experiencing a *de novo* anterior MI and qualify based on inclusion/exclusion criteria will be approached for enrollment. Eligible subjects will be randomized to receive one of three possible intracoronary treatments: Investigational product at 12.5 M or 25.0 M allogeneic MPCs or saline placebo control.

Randomization will occur after informed consent has been obtained and the PCI with stenting of the culprit LAD coronary artery lesion has been successfully completed (residual TIMI Flow Grade 3 or 2, residual diameter stenosis <20% by QCA, uncomplicated primary PCI).

The randomization and treatment assignment will be obtained from an IVRS/ IWRS.

The following stratification for duration of cardiac ischemia will be performed to ensure balanced randomization across the treatment groups:

- ≤ 2 hours
- >2 hours to ≤ 6 hours
- >6 to ≤ 12 hours.

After randomization has been performed, each subject will receive a unique identification number that will include site and subject identifiers.

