8.2 Secondary Efficacy Endpoints

- The change in LVESV as assessed by 2D-echocardiography from baseline to 6 months post investigational agent infusion.
- The change in relative infarct size as assessed by late contrast enhancement MRI (% infarct volume/total LV tissue volume) from baseline to 6 months post investigational agent infusion.
- Additional functional efficacy endpoints will be assessed with the following diagnostic studies:
 - Cardiac MRI at 2-4 days, 30 days and at Month 6.
 - LVEF
 - LVESV
 - LVEDV
 - Left ventricular wall thickness and thickening in all segments including infarct area
 - Regional wall motion score
 - Myocardial MVO measured as reduced signal intensity in the region of interest
 - MI size measured in the region of interest as late contrast enhancement
 - Myocardial salvage index
 - 2D echocardiogram at 2-4 days, 30 days and at Month 6.
 - LVEF
 - LVESV
 - LVEDV
 - Cardiac dimensions (LVESD/ LVEDD)
 - Regional wall motion score index
 - If neither MPC arm is found to be better than the placebo arm and there is no difference between the MPC groups (using the ANCOVA test with alpha=.1) in the effect on LVESV then the pooled MPC group will be compared to the placebo group for all functional parameters.
 - A subset analysis that corresponds to the stratification used during randomization will be performed. Stratification will be based on the following following categories defined as time from onset of AMI symptoms to PCI:
 - ≤ 2 hours
 - > 2 hours to ≤ 6 hours
 - > 6 to ≤ 12 hours.

- In addition, a subset analysis will be evaluated at the following ischemia duration time points:
 - ≤ 6 hours
 - > 6 to ≤ 12 hours.
- NT-Pro-BNP serum levels (as measurement biomarker for heart failure) at baseline, days 2-4 and 30 and months 3 6, 12 and 24
- Score changes for TIMI Myocardial Flow Grade and Perfusion assessments at the following day 0 time points:
 - pre-PCI,
 - immediately post-PCI,
 - after approximately 50% of intracoronary infusion of investigational agent,
 - at completion of intracoronary infusion of investigational agent.

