10. ASSESSMENT OF FEASIBILITY

10.1 Feasibility Endpoint

Feasibility of the infusion of the investigational agent will be monitored by measurement of TIMI Flow prior to, during (approximately 50% of total investigational agent volume infused), and following the investigational agent infusion after successful PCI and stenting.

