11.2 Statistical Methods

The primary efficacy analysis will use an ANCOVA model with baseline LVESV as covariate and alpha=0.05 to test for a difference of change in LVESV from baseline to Month 6 between each MPC arm separately and the placebo arm. If neither MPC arm is found to be better than the placebo arm and there is no difference between the MPC groups (using the ANCOVA test with alpha= 0.1) in the effect on LVESV, then the pooled MPC group will be compared to the placebo group for all functional parameters.

All other statistical tests will be considered to be exploratory (post-hoc) unless a pre-specified hypothesis exists in the statistical analysis plan (SAP), which will be finalized prior to any analysis. All statistical tests will be two-sided and statistical significance will be assessed with

respect to a nominal p-value ≤ 0.05 . Any deviations from the planned analyses will be documented and justified in the final clinical/statistical study report.

The primary efficacy analysis for LVESV will be performed using cMRI collected data. The secondary efficacy analyses for LVESV will be performed using ECHO data alone, as well as ECHO data as a substitute for missing cMRI data at baseline and/or at Month 6.

In the latter case, a regression equation will be determined between measurements for LVESV-cMRI and LVESV-ECHO over a range of values. Whenever appropriate and based on LVESV-ECHO values generated using the regression equation, a LVESV-ECHO “corrected” value will be determined and used as a replacement for missing value for LVESV-cMRI.

When all enrolled subjects have completed the study through Visit 9 (Month 6), an unblinded analysis of the safety and primary and secondary efficacy endpoints will be conducted.

The primary and secondary efficacy analyses will be performed using data collected through Visit 9 (Month 6). In addition, safety analyses will be performed on all available data through Visit 12 (Month 24) at the time of conduct of the efficacy analysis. In addition, the final safety analysis will be performed at 24 months for all patients.

No additional efficacy data will be collected beyond Visit 9 (Month 6) except for cardiac biomarkers.

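### Controlling the CMH test by about 25 unpooled sites as well as ischemia time leaves strata too sparse for about 105 subjects and costs power; ischemia time alone costs almost none

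*Combined protocol and SAP*

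**What the plan says.** Section 11.8 sets the test for treatment differences in categorical measures: "The Cochran-Mantel-Haeszel test (CMH) controlled by site and the time from the onset of AMI symptom to PCI will be used". The rank option in the same section is permissive and covers a different kind of measure: "For non-normally distributed measures, the Wilcox-Mann-Whitney test or analysis of variance ANOVA of rank transformed data may be used as an alternative". A rank analysis of TIMI score changes (section 8.2) is therefore open, but for categorical measures the CMH test is the one the plan commits to.

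The trial size is given in section 5: "approximately 105 subjects at approximately 25 clinical sites". Allocation is 1:1:1, about 35 per arm (section 4.3). Randomization is balanced on one named factor, in section 7.5: "The following stratification for duration of cardiac ischemia will be performed to ensure balanced randomization across the treatment groups". That factor has three categories (up to 2 hours, over 2 to 6 hours, over 6 to 12 hours). Site is not named as a randomization factor.

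Feasibility belongs to the primary objective in section 4.1 ("The primary objective of this study is to determine the safety and feasibility of intracoronary allogeneic"). Section 10.1 ties it to a graded angiographic scale: "Feasibility of the infusion of the investigational agent will be monitored by measurement of TIMI Flow prior to". Section 11.8 designates a primary feasibility analysis in the Full Analysis population.

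The visible text does not say whether site and time are crossed, how time is coded for this test, which arms are compared, or whether small sites are pooled.

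**The concern.** The CMH test compares arms within each stratum and adds up the results. A stratum with subjects from only one arm contributes zero to both numerator and variance, so those subjects drop out of the test. Controlling for two factors ordinarily means forming strata from their combinations. At about four subjects per site over three arms, many of those strata cannot hold both arms of a comparison.

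At stake is the plan's one committed test of whether categorical measures such as TIMI flow differ between cell infusion and placebo. Followed as written, it uses the information of a much smaller trial, although the subjects are there and a stratification matching the randomization would keep almost all of it.

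**Working it through.** **The plan's own figure.** The only sample-size statement (section 11.5) is for LVESV: difference 10 ml, SD 14 ml, two-sided 5%, power 80%, about 4% dropout. A two-sample t-test gives 32 per arm; 32/0.96 = 33.3, so 34 per arm and 102 in total, close to the stated 105. No power or event rate is stated for any categorical measure, so there is no figure to reproduce for the CMH test.

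**Sparsity, from the documents' numbers.**
- Subjects per site: 105/25 = 4.2.
- Crossed strata: 25 × 3 = 75 at most.
- Subjects per stratum: 105/75 = 1.4 over three arms; 70/75 = 0.93 for one dose against placebo.

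**Information measure.** With n1k and n0k subjects per arm in stratum k and a common event rate, the expected CMH variance is proportional to the sum over k of n1k·n0k/(n1k + n0k). Unstratified, one dose against placebo gives 35 × 35/70 = 17.5, and pooled MPC against placebo gives 70 × 35/105 = 23.3. The retained share is the stratified sum divided by this value.

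**Simulation assumptions (not in the documents).** 105 subjects, 1:1:1, permuted blocks of 6 within ischemia category, site not a randomization factor. Site weights equal, gamma(1) or gamma(0.5). Time split 33/33/33, 20/60/20 or 15/70/15. Binary outcome, two-group CMH without continuity correction, two-sided 5%, 2,000–3,000 trials per scenario.

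| Strata | Retained, one dose vs placebo | Retained, pooled MPC vs placebo |
|---|---|---|
| 25 sites × 3 time categories | 0.357–0.630 | 0.470–0.705 |
| 25 sites × 2 time categories | 0.490–0.708 | 0.607–0.775 |
| 15 sites × 3 time categories | 0.509–0.726 | 0.628–0.788 |
| 15 sites × 2 time categories | 0.642–0.794 | 0.743–0.844 |
| 25 sites, no time | 0.671–0.792 | 0.770–0.848 |
| 3 time categories only | 0.998–0.999 | 0.998–0.999 |

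In the first row, one dose against placebo works like an unstratified comparison of 35 × 0.357 = 12.5 to 35 × 0.630 = 22 subjects per arm. On average 33–57 of the 75 strata were occupied, and 31–62% of the subjects in that comparison sat in one-arm strata.

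**Power, 25 sites × 3 categories against time only.**

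| Comparison | Assumed rates | As written | Time only |
|---|---|---|---|
| One dose | 5% vs 30% | 34–61% | 81–84% |
| One dose | 5% vs 15% | 7–17% | 26–31% |
| One dose | 5% vs 10% | 3–7% | 11–12% |
| Pooled MPC | 5% vs 30% | 58–79% | 90–92% |
| Pooled MPC | 5% vs 15% | 13–22% | 27–32% |

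**Type I error, one dose.** Both arms at 15%: 3.3–5.4% as written, 4.3–5.6% time only. Both arms at 5%: 0.6–2.9% and 2.5–4.3%.

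**Sensitivity.**
- Other accrual patterns (exactly even, random, or skewed with gamma(1) site weights; 4,000 trials per scenario), one dose at 5% vs 30%: crossed 27–53%, site only 61–70%, time only 83–85%.
- Other rates, same set: 10% vs 40%, crossed 40–56% against 85–86%; 30% vs 62%, crossed 35–48% against 77–79%.
- Between-site differences (logit SD 1), one dose at 5% vs 30%: crossed 35–64%, time only 79–82%, with time-only Type I error 4.0–5.2%.
- Three-arm CMH test (2 df), 5% in placebo against 30% in both doses, 1,500 trials per scenario: information lost 30–53%, power 43–65% against 82–86%.
- Pooling small sites into one group, three time categories kept: with sites under 12 subjects pooled, the loss falls to 0.2–12% (one dose) and 0.1–8% (pooled MPC); with sites under 6 pooled, it is still 19–28% and 14–20%.

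**The case against.** The strongest reply is that section 11.8 never says the factors are crossed, and that time coding, comparison and pooling are ordinary SAP content still to be written. Section 11.2 makes tests other than the primary analysis exploratory unless the SAP pre-specifies a hypothesis. Section 11.9 rules out testing of safety measures, so TIMI flow reported as safety is not tested at all. Relative risks and confidence intervals are reported alongside the CMH test. No stated power is missed, and there is no pass/fail threshold for TIMI flow. Site adjustment is also a legitimate multicentre choice for an operator-dependent measure.

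Much of this stands. The figure of 75 is a ceiling, only the direction of the loss follows from the documents, and the two-group results for one dose are the least favourable comparison. At 5% vs 15% even the time-only test has power of just 26–31%. With about 35 per arm, a non-significant result would not show absence of a difference under either version.

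It does not remove the point. Every reading examined that keeps unpooled sites loses material information: site alone, two time categories, 15 enrolling sites, and the three-arm test. The site-adjustment argument did not reverse the result at the one level of between-site variation tried. That the SAP is still to be finalized is a reason to settle this now.

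**Conclusion.** The concern holds. Followed as written with unpooled sites, the CMH test is materially weaker than one stratified by the randomization categories. With 25 sites crossed with three time categories, the loss of information is 37–64% for one dose against placebo and 30–53% for pooled MPC, against 0.1–0.2% for ischemia time alone. Two time categories and/or 15 enrolling sites still lose about 16–51% across both comparisons; site alone loses 21–33% and 15–23%. These figures are illustrative, not bounds: they rest on assumed accrual by site and time, and the power figures also on assumed event rates. The ordinal form of the test was not simulated, though one-arm strata carry no information there either.

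The cost is power, not validity, and the consequence is limited because the test is exploratory by default and estimates are still reported. The LVESV ANCOVA and the sample size of 105 are unaffected. The change should be made because it is nearly free and feasibility is part of the primary objective. Confidence is medium.

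**What to change.** In section 11.8 and the SAP, stratify the CMH test by the three randomization categories of ischemia time only, name the arms compared, and present results by site descriptively. The downside is no adjustment for between-site differences in this test.

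If site is kept, pre-specify a pooling rule that prevents strata this sparse. In simulation a 12-subject cut-off removed most of the loss and a 6-subject cut-off did not. At 4.2 subjects per site on average, the 12-subject rule left at most about 2.6 of 25 sites unpooled on average, so it comes close to dropping site. The cut-off should be checked against actual accrual before unblinding.

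The cost is one sentence in section 11.8 and one in the SAP, which section 11.2 says is finalized before any analysis. No extra data or patients are needed.
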